2. INTRODUCTION

2.1. Background & Rationale

Skin acts as a defensive physical barrier against multiple detrimental external forces such as mechanical trauma, noxious irritants, infectious pathogens, and excessive fluids. However, prolonged exposure of the skin to different sources of moisture such as urine or stool, perspiration, wound exudate, secretions including mucus and saliva, and their contents can compromise the integrity of this barrier.²

Moisture, in the form of sweat, which gets trapped in the skin folds and other skin-on-skin contact areas due to lack of air circulation, can lead to overhydration and maceration of skin. Maceration increases friction between opposing skin surfaces, which leads to inflammation, presenting initially as minimal erythema of the skin folds.³ The signs and symptoms of such skin inflammation are gradual in onset, including itching, pain, burning, prickling, or stinging sensations in the intertriginous areas. Initial presentation involves mild erythematous patches mirrored on both sides of the intertriginous areas, but the lesions can quickly progress to exudative erosions, fissures, maceration, or crusts.⁴ In addition, development of a secondary cutaneous infection by bacteria or fungi may be suggested by worsening erythema, pustules or vesicles, satellite lesions, or malodor.^{5,6,7}

This type of chronic irritation of the intertriginous areas is commonly seen in bed-ridden or elderly individuals, and infants, due to reduced immunity, immobility, and incontinence.⁶ Infants are also susceptible to this skin condition as a result of drooling, short neck structure with prominent skin folds, and flexed position.^{3,5,8} Obesity and hyperhidrosis are also considered important risk factors, with other predisposing factors being diabetes, urinary or fecal incontinence, poor personal hygiene, malnutrition, immunosuppression, occlusive clothing, and a hot and humid climate.

Management of such skin fold conditions typically focuses on removal of predisposing factors, including minimizing moisture and friction in the involved areas. This is followed by topical or systemic antimicrobial (antibacterial or antifungal) agents as well as low-potency corticosteroids if required.^{5,7} Preventive measures are important as they may help not only with management of current skin fold conditions, but also to avoid future episodes.^{6,7}

This study will evaluate the efficacy of a skin protectant textile (SPT) to manage skin fold conditions in participants over a five-day treatment period. Healthcare providers (HCPs) will apply the SPT to the target area(s) of the participants. As part of the participant screening process, the PI or qualified designee will examine and document the skin fold conditions to identify potential target area(s) before the SPT is first applied (Day 0) to these area(s). The PI or qualified designee will also take photographs of the target areas on Day 0, and on Days 1, 3, and 5 (or the last day of study participation [ie, fully healed target area(s)]), during SPT changes. These photographs will be used by a third-party clinician to assess the status of erythema, maceration, denudation, and satellite lesions in the target areas. The PI or qualified designee will assess moisture and odor, and participants will appraise discomfort (pain, itching, and burning) in the target area(s) on the same days as the target area photography. The study will also include HCP feedback regarding their experience with the SPT, and a survey about overall experience of the participants with the SPT.

2.2. DriGo-HP™ (referred to as “Skin Protectant Textile [SPT]”)

DriGo-HP™ (formerly known as the “Stay Fresh® Skin Fold Management Textile” [#MSCWH219S]; referred to as “Skin Protectant Textile [SPT]”) is designed for use in skin-to-skin contact areas. It is made of a soft, thin, smooth polyester fabric that helps manage moisture, reduce friction, and provide comfort

Page 12 of 28

and odor control. It is designed to wick moisture away from the skin fold and keep it dry. The moisture from the skin fold is translocated towards the external edge of the fabric where it is dispersed by evaporation.

In addition, the SPT uses a unique, patented technology where hydrogen peroxide (H_2O_2) is encapsulated in a binder leading to its slow release over time when exposed to moisture. H_2O_2 is a known germicidal agent, which prevents the growth of bacteria such as *Escherichia coli* (*E. coli*) and Methicillin-Resistant *Staphylococcus aureus* (MRSA) in the textile throughout the duration of the product's use. H_2O_2 is used in the product at a concentration no greater than 0.3%, released slowly over time. SPT can be left in place for up to five days, depending on soiling, odor, amount of moisture, and condition of the skin.

2.3. Risk/Benefit Profile

2.3.1. Potential Study Risks

The participant may experience an allergic reaction to the fabric of the SPT, H_2O_2 , or the tape used to secure the SPT. To minimize participant risk, screening will be done for any known allergy or sensitivity to these components. Furthermore, the participants will be under the care of a physician who will take timely measures to address and mitigate any adverse reactions should they occur. The PI or qualified designee and the HCPs will be at minimal risk during the study. Care of skin fold conditions is a conventional task in these clinical settings; the SPT is a commercially available product; and the PI or qualified designee and the HCPs will be wearing gloves as they make assessments for moisture or odor of the target areas, or during application of the SPT to the target areas of the participants, respectively.

2.3.2. Potential Study Benefits

The participants may benefit from faster resolution of their skin fold conditions, which may lead to enhanced level of comfort. Furthermore, HCP feedback and participant survey may help enhance understanding as regards experience with the SPT. No prescription is required to use the SPT; therefore, the study data may also benefit non-clinically trained consumers who may be able to use the SPT to treat skin fold conditions. The PI or qualified designee and HCPs will not benefit from the study directly.

2.3.3. Assessment of Potential Risk/Benefit Profile

The use of this currently marketed SPT presents minimal risk to the participants, the PI or qualified designee and the HCPs while offering the potential for benefit to the participants enrolled in the study. Therefore, the risk-benefit profile for the study is acceptable.

3. OBJECTIVES AND ENDPOINTS

OBJECTIVES	ENDPOINTS	JUSTIFICATION FOR ENDPOINT(S)
Primary		
To evaluate the efficacy of SPT to improve skin fold conditions.	1. Improvement in skin fold conditions such as erythema, maceration,	1a. This endpoint addresses the objective

OBJECTIVES	ENDPOINTS	JUSTIFICATION FOR ENDPOINT(S)
	
denudation, satellite lesions, odor, pain, itching, and burning over five days of treatment.
 
1a. Likert scales developed for erythema, maceration, denudation, and satellite lesions. Scoring of the target area(s) done by a third-party clinician using the Likert scale(s) and photographs taken by the PI or qualified designee on Day 0, and on Days 1, 3, and 5, during SPT changes.
 
1b. Assessment of odor in the target area(s) on Day 0, and on Days 1, 3, and 5, during SPT changes, using a Likert scale.
 
1c. Participant assessment of discomfort (pain, itching, and burning) assessment using a VAS on Day 0, and on Days 1, 3, and 5, during SPT changes. Participants will also be asked to identify the most prominent type of discomfort in the skin fold: pain, itching, or burning.
	
assessment of erythema, maceration, denudation, and satellite lesions by a third-party clinician.
 
1b. This endpoint evaluates the assessment of odor, which may be an indicator of infection, in the target areas during the use of SPT.
 
1c. This endpoint addresses the participants' perception of discomfort in the target area(s), while also evaluating which symptom, pain, itching, or burning is the most prominent over the duration of SPT use.

Secondary		

1. To gather PI or qualified designee's assessment of moisture control in the target areas.2. To assess HCP feedback on the SPT.3. To assess the overall participant experience with the SPT.	
1. PI or qualified designee survey responses for moisture in the target area(s) on Day 0, and on Days 1, 3, and 5, during SPT changes, using a Likert scale.2. HCP survey responses on Day 5 regarding feedback about the SPT, using a VAS.3. Participant responses on Day 5 regarding their experience with the SPT, using a VAS.	
1. This endpoint evaluates the assessment of moisture present in the target areas during the use of the SPT.2. This endpoint evaluates HCPs' feedback about the SPT and may influence their future use of the SPT in clinical practice.3. This endpoint evaluates participants'

OBJECTIVES	ENDPOINTS	JUSTIFICATION FOR ENDPOINT(S)
		experience with the SPT.

Note: All endpoint-related activities planned for Day 5 will be carried out for the last day of study participation (ie, fully healed target area[s]) if it occurs before Day 5.

4. STUDY DESIGN

4.1. Overall Design

This is a prospective unblinded study in which the effectiveness of the SPT in the management of participants with skin fold conditions such as erythema, maceration, denudation, satellite lesions, pain, itching, burning, moisture, and odor will be evaluated. As part of the screening process, the PI or qualified designee will examine and document the skin fold conditions to identify potential target area(s) prior to application of the SPT to these areas (Day 0). The PI or qualified designee will take photographs of the target areas using a wound camera system once the participants are enrolled in the study (Day 0). The HCPs will apply the SPT to the target area(s) of the participants as described in the Instructions for Use (IFU). The PI or qualified designee will again take photographs of the target areas using the wound camera system on Days 1, 3, and 5 (or the last day of study participation [ie, fully healed target area(s)]), during SPT changes. On days when the target areas are photographed, the PI or qualified designee will also assess moisture and odor using Likert scales, and participants will provide their impressions of pain, itching, and burning in the target area(s) using a VAS survey. Participants will also be asked to identify the most prominent type of discomfort during this assessment. On Day 5 or the last day of study participation (ie, fully healed target area[s]), as applicable, VAS surveys will be used for the following: (1) HCP feedback about the SPT, and (2) Overall participant experience with the SPT. After the participants are dismissed from the study, a third-party clinician will score the status of erythema, maceration, denudation, and satellite lesions in the target areas using the photographs taken by the PI or qualified designee and the Likert scales developed for the study.

4.2. End of Study Definition

The study will be considered complete after the participants are dismissed upon completion of all study-related activities, the third-party clinician has assessed 119 target areas, and a Clinical Study Report approved by the Clinical Affairs Director has been issued.

5. STUDY POPULATION

Participants can be the source of up to two target areas, and each target area can have more than one skin fold condition. Per the assessment of the PI or qualified designee, the skin fold conditions of the participants must be anatomically distant enough to allow the participants to make an objective assessment of discomfort (pain, itching, and burning) in each target area. A participant may be re-enrolled using a new participant study identification (ID) number for another set of up to two target areas at a different location. The target areas must be anatomically distant (per the assessment of the PI or qualified designee), as described above.

5.1. Inclusion Criteria

Individuals who meet all of the following criteria will participate in this study:

- Individuals \geq 18 years of age.
- Individuals who have evidence of one or more of the following skin fold conditions: erythema, maceration, denudation, satellite lesions, pain, itching, burning, moisture, and odor.
- Individuals whose treatment plan permits assessment of the skin fold condition(s) for up to six days.

5.2. Exclusion Criteria

Individuals who meet any of the following criteria will not be eligible to participate in this study:

- Individuals whose target area(s) are being managed with topical treatments such as antibiotics, antifungals, ointments including skin protectants, anti-itch products, anoperineal dressings or absorbent pads (eg, ARD®).
- Individuals with a known allergy or sensitivity to the ingredients in the SPT, such as the fabric or H₂O₂, as well as the tape that may be used to secure the SPT.
- Individuals who are pregnant or are breastfeeding.

5.3. Strategies for Recruitment and Retention

The PI at the study site will recruit potential participants from the current patient population being treated at the facility who satisfy the inclusion/exclusion criteria. The PI will inform the participants that they are free to withdraw from the study at any time and that it will not affect their treatment in any way. For this study, advertisements of any kind or a database to look up potential participants will not be used.

Retention will ideally be managed by targeting participants who are anticipated to require at least five days of SPT treatment.

5.4 Early Withdrawal and Replacement

Participants whose skin fold conditions are healed prior to Day 5 will be considered to have complete data.

Participation in the study may end at several critical points:

- Participant withdraws from the study for any reason, including when the target area(s) have not healed but the participant is discharged due to resolution of the medical condition for which the participant was hospitalized.
- Participant is not compliant with study procedures.
- Participant presents with adverse event(s) such that, in the opinion of the PI, it is in the best interest of the participant to discontinue study participation.
- Protocol violation requiring discontinuation of use of the study product(s).

Based on the above reasons, if any participant withdraws from the study or is dismissed, additional participant(s) will be recruited such that the total number of target areas included in the study will be 119.

6. STUDY PROCEDURES AND ASSESSMENTS

6.1. Informed consent and screening (Day 0)

6.1.1 Informed Consent

The PI or qualified designee will obtain written informed consent from all participants. Written informed consent must be documented on an Informed Consent form (ICF) that has received approval by an IRB/Ethics Committee. The ICF must be written in adherence to GCP and Good Documentation Practices (GDP), and must comply with all elements required by United States (US) Food and Drug Administration (FDA) 21 CFR 50.25 and International Conference on Harmonisation (ICH) 4.8, state and local regulations, and additional elements relevant to specific study situations (including a statement that Medline Industries, Limited Partnership [LP], henceforth referred to as "Medline"), and relevant authorities have access to participant records). A copy of the signed consent will be given to each participant.

6.1.2 Verification and Eligibility

Following informed consent, the participants will undergo screening based on the inclusion/exclusion criteria detailed in Sections 5.1 and 5.2, and will receive a unique screening number that will be recorded in the Participant Screening Form (PSF). The PI or qualified designee will examine potential target area(s) of the participants and document the skin fold conditions such as erythema, maceration, denudation, or satellite lesions in the PSF. As part of this process, the PI or qualified designee will obtain a medical history of the participants' target area(s) and document concomitant medications such as pain medications, systemic antimicrobials, systemic steroids, and topical treatments being administered to the target areas.

Potential participants who satisfy all inclusion/exclusion criteria for the study will be enrolled and will receive unique participant study identification (ID) numbers based on the order in which they are enrolled after being screened. Demographic information of the participants will be documented in the PSF. Case Report Forms (CRFs), PSF, and other study-related documents will be provided separately to the PI or qualified designee, and the HCPs.

Note: A participant may be re-enrolled using a new participant study ID number for another set of up to two target areas at a different location.

6.2. Evaluation of the Study Product

6.2.1 Initial Assessment (Day 0)

6.2.1.1. Photographic Documentation to Assist Third-Party Clinician in Assessment of Erythema, Maceration, Denudation, or Satellite Lesions in Target Areas

The PI or qualified designee will photograph the skin fold conditions in the target area(s) using the wound camera system.

6.2.1.2. Assessment of moisture and odor in the target areas

The PI or qualified designee will assess moisture and odor in the individual target area(s) of the participants using study-specific Likert scales developed for these parameters.

6.2.1.3 Assessment of discomfort in the target areas

Participants will assess discomfort (pain, itching, and burning) in the target areas using a VAS survey. They will be asked to mark a point on the VAS using a pen such that the point reflects their perception of discomfort. The PI or qualified designee will measure the distance between the start of the line (the left side of line) and the point marked by the participants, using a calibrated ruler. The measured value will be recorded in the survey.

Participants will also be asked to identify the most prominent type of discomfort in the target area: pain, itching, or burning. The response will be recorded in the CRF.

6.2.1.4. Application of SPT on Day 0

The HCPs will apply the SPT to the target area(s) of the participants per the IFU.

6.2.2. Assessments on Days 1, 3, and 5 (or Last Day of Study Participation [ie, healed target area(s)])

6.2.2.1 Assessments

The HCPs will remove the SPT from the target areas and perform the assessments as detailed in Section 6.2.1.1–6.2.1.3 will be performed. Any additional care of the target areas given by the HCPs will be documented in the CRF.

6.2.2.2. Application of SPT

After performing the assessments and care in Section 6.2.2.1, the HCPs will apply a fresh SPT to the target area(s).

Note: On Days 2 and 4, the PI or qualified designee may examine the target areas, but no study-related assessments will be performed, unless it is the last day of study participation. The SPT in the target areas may be changed per assessment by the PI or qualified designee. This may also occur on Days 1, 3, and 5 in addition to the scheduled application of the SPT.

6.2.3. Additional Study Activities on Day 5 (or Last Day of Study Participation [ie, fully healed target area(s)])

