6.3. End of participant activity

The HCPs will remove the SPT from the target areas of the participants after all study activities have been completed. Thereafter, the participants will be dismissed from the study.

If the skin fold conditions in the target area(s) of any participant resolve before Day 5, the last day of study participation will occur on that day (earlier than Day 5). All activities planned for Day 5 should be carried out on the last day of study participation in order for participants to have complete data.

Note: Should the PI or qualified designee determine that continued treatment of the skin fold condition(s) beyond five days is necessary, such treatment must be administered per hospital procedures and using materials from hospital inventory. Study materials must be reserved for up to six days of participant enrollment.

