8. STATISTICAL CONSIDERATIONS

8.1. Sample Size Determination

The sample size of 119 skin fold conditions was selected to detect a minimal clinically significant difference of 10 in the VAS pain scale between days of SPT changes with an estimated standard deviation of 30 and a Bonferroni adjusted α of $\alpha = .0083$ at 80% power, using the “Paired Wilcoxon Signed-Rank Test” procedure in PASS 2021 Power Analysis and Sample Size Software (2021). NCSS, LLC. Kaysville, Utah, USA, ncss.com/software/pass). It is noted that participants may have skin folds with independent skin fold conditions. One participant may be the source of, at most, two skin fold conditions for the purposes of this study. The candidate skin fold conditions must be, in the assessment of the PI or qualified designee, anatomically distant enough to permit objective assessment of discomfort (pain, itching, and burning) in each target area by the participant. In the event that a participant withdraws from the study, additional participants will be enrolled to achieve a final number of 119 target areas with complete data and until adequate power for analysis has been reached.

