8.8. Missing Data

All attempts will be made to collect all data per protocol. Any data point that appears to be erroneous or inexplicable based on clinical judgement will be investigated as a possible outlier. In general, values for missing data will not be imputed unless methods of handling missing data are specified in this section or relevant sections.

For the analyses of all primary and secondary objectives, observations with missing clinical ratings (ie, rating of erythema by a third-party clinician) or self-reported ratings (ie, VAS score of participant experience) will be dropped from the analysis of variable of interest.

All missing data will be quantified in the final report and possible biases for any missing data will be reported.

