8.9.1 Analysis of Primary Endpoints

The primary goal of this study is to evaluate the efficacy of the SPT to improve skinfold conditions, including erythema, maceration, denudation, satellite lesions, pain, itching, burning and odor over five days of treatment. Erythema, maceration, denudation, satellite lesions, and odor will be assessed using Likert scales, with "0" being least severe and "4" being most severe. Ordinal mixed models, or other appropriate methods depending on the distribution of data, will be employed to compare the assessment of skin fold

conditions of target areas across five days of treatment, with participants as a random variable and treatment days (Day 0, and Days 1, 3, and 5) as a covariate. Significant omnibus test will be followed by Tukey's post-hoc pairwise comparisons of Day 0 vs Day 1, Day 0 vs Day 3, Day 0 vs Day 5, Day 1 vs Day 3, and Day 3 vs Day 5.

ANOVA/Mixed models, or other appropriate methods depending on the distribution of data, will be conducted to compare VAS scores of discomfort (pain, itching, or burning) reported by participants on Day 0, and Days 1, 3, and 5. Significant omnibus test will be followed by Tukey's post-hoc pairwise comparisons of Day 0 vs Day 1, Day 0 vs Day 3, Day 0 vs Day 5, Day 1 vs Day 3, and Day 3 vs Day 5. In addition, descriptive statistics for the most prominent discomfort in the target area will also be reported in this study.

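### Areas that heal by Day 2 have no Day 3 score because they healed, and the analysis sections do not say how their last-day score enters the Day 0/1/3/5 model

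*Combined protocol and SAP*

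**What the plan says.** - **Assessment days.** Scores are taken on Days 0, 1, 3 and 5. On Days 2 and 4, section 6.2.2.2 says "no study-related assessments will be performed, unless it is the last day of study participation".
- **Early healing.** Section 6.3 makes the day of resolution the last day of participation and moves the Day 5 activities to it. Section 5.4 adds: "Participants whose skin fold conditions are healed prior to Day 5 will be considered to have complete data".
- **Where the last-day score belongs.** The Schedule of Activities (1.2) has one column for Day 5 or the last day. The notes in the Synopsis and section 3, and the endpoint list in 8.6.1, treat the last day as the alternative to Day 5.
- **Primary model.** Section 8.9.1 uses mixed models. For the Likert outcomes these have participant as the random effect and "treatment days (Day 0, and Days 1, 3, and 5) as a covariate". Five pairwise contrasts follow: 0 vs 1, 0 vs 3, 0 vs 5, 1 vs 3 and 3 vs 5. No rule is given for a score taken on Day 2 or 4, or for scheduled days after healing.
- **Missing data.** Section 8.8 imputes nothing unless a method is specified, and none is. Observations with missing ratings "will be dropped from the analysis of variable of interest".
- **Analysis population.** Section 8.3 restricts the analysis to participants who complete five days of treatment with complete data.

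**The concern.** An area that heals by Day 2 is among the best responders, and it is absent from Day 3 for that reason. The areas observed at Day 3 are then a less improved set than those at Days 0, 1 and 5. Any contrast involving Day 3 partly reflects who is still present.

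The plan also leaves the coding open. One analyst could enter a Day 2 healed score as Day 5, another could drop it as off schedule, and a third could carry it to Days 3 and 5. A score from an area that heals on Day 3 could count as Day 3, as Day 5 or as both. Each choice gives different primary results, and the choice could be made after the data are seen.

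**Working it through.** **1. The plan's own figure.** Inputs from section 8.1: difference 10, SD 30, alpha 0.0083 (0.05/6), power 80%, "Paired Wilcoxon Signed-Rank Test". Sidedness is not stated.
- Normal approximation, two-sided: n = (z₁₋α/₂ + z₀.₈₀)² × (30/10)² = (2.640 + 0.842)² × 9 ≈ 109.1.
- Noncentral t: 113.
- Signed-rank adjustment for normal data: 113 × π/3 = 118.3; solving directly on the adjusted scale gives 118. This agrees with the stated 119 to within one. One-sided gives 102.

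The calculation thus rests on 119 complete pairs between two days of SPT change. If 5%, 10%, 20% or 30% of areas heal by Day 2 and have no Day 3 score, 113, 107, 95 or 83 pairs remain for a paired Day 3 comparison. Power is then 77.8%, 74.9%, 68.2% or 60.3%. A mixed model also uses incomplete areas, so these figures describe the paired test only.

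**2. Which scores exist, by day of healing** (where healing ends participation)

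| Healed on | Day 1 | Day 3 | Last-day score |
|---|---|---|---|
| Day 1 | yes | none | Day 1 |
| Day 2 | yes | none | Day 2, no matching model day |
| Day 3 | yes | yes | Day 3 |
| Day 4 | yes | yes | Day 4, no matching model day |

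**3. Direction.** Let p be the share healed by Day 2, U the mean Day 3 score of the other areas and H that of the healed areas. The true Day 3 mean is (1 − p)U + pH. The observed mean is U, which is too high by p(U − H). Day 0 vs 3 and Day 1 vs 3 therefore shrink, and Day 3 vs 5 grows. A mixed model removes part of this error by using each area's other days. If every area has a Day 0 and a Day 5 value, Day 0 vs 5 does not change.

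**4. Size with gradual healing (assumed).** VAS simulation: 6,000 areas, one per participant; fall per day of mean/SD 4/4, 7/6 or 10/8 mm; an area counts as healed at 3 mm or below and stays at 0. Random-intercept model with day as a factor. Healed by Day 2: 9%, 14% and 22%. Improvement in mm:

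| Coding | 0 vs 3 | 0 vs 5 | 1 vs 3 | 3 vs 5 |
|---|---|---|---|---|
| True values; also healed score carried forward | 12.2, 19.3, 24.6 | 18.4, 26.9, 31.5 | 7.9, 12.2, 14.7 | 6.3, 7.6, 6.9 |
| Last-day score also used as Day 5 | 11.8, 18.9, 24.1 | 18.4, 26.9, 31.5 | 7.6, 11.8, 14.2 | 6.6, 8.0, 7.4 |
| Last-day score moved to Day 5 only | 11.1, 16.8, 20.3 | 18.4, 26.9, 31.5 | 7.4, 10.7, 11.9 | 7.3, 10.1, 11.2 |
| Day 2 and 4 scores dropped | 12.0, 19.3, 24.8 | 18.1, 26.5, 30.6 | 7.8, 12.2, 14.9 | 6.2, 7.2, 5.8 |
| Five-day completers only | 10.9, 15.6, 17.6 | 17.9, 25.4, 28.2 | 7.3, 10.4, 11.7 | 7.0, 9.9, 10.7 |

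- Last-day score also used as Day 5: the error is 0.3 to 0.5 mm.
- Last-day score moved off Days 1 and 3: Day 3 vs 5 is overstated by 1.0 to 4.3 mm (for example 11.2 − 6.9).
- Off-schedule scores dropped: Day 3 vs 5 is understated by 0.1 to 1.1 mm, so the direction reverses. Day 0 vs 5 is understated by 0.3 to 0.9 mm.
- Early healers excluded, as section 8.3 can be read: Day 0 vs 5 is understated by 0.5 to 3.3 mm and Day 0 vs 3 by 1.3 to 7.0 mm.

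**5. Size with abrupt healing (assumed).** 3,000 areas; Day 0 mean 45, between-area SD 17, residual SD 10; unhealed areas fall 3 mm/day; healed areas are near 0 by Day 2. Healing is unrelated, partly related or fully related to baseline severity. The last-day score is used as Day 5.
- 10% healed by Day 2: Day 3 to 5 is −6.1 to −7.8 against a true −5.1 to −5.2.
- 20% healed: Day 3 to 5 is −7.2 to −9.7 against −4.5 to −4.7; Day 1 to 3 is −5.9 to −7.2 against −8.4 to −12.3.

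A separate run with the same coding gave Day 3 vs 5 errors of about 0.1 to 0.5 mm at 2% healed, 1 to 2.6 mm at 10% and 2.7 to 5.3 mm at 20%.

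**The case against.** The best defence is that the plan already points to an answer. Sections 1.2, 3 and 8.6.1 and the Synopsis all treat an early last day as the Day 5 assessment. On that reading Day 0 vs 5, the contrast over the whole treatment period, is sound, and a mixed model softens the rest. Section 5.3 aims to recruit people expected to need at least five days of treatment, which argues against many areas healing by Day 2. All of this stands. It limits the size of the problem but does not supply the missing rule.

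A reader might infer more than the documents support:
- **That every early healer lacks a Day 3 score.** Areas healing on Day 3 or 4 have one. So may an area healed by Day 2 if its participant stays in the study because a second area has not healed.
- **That Day 2 and Day 4 scores have no place in the model.** The documents suggest the Day 5 slot. What is missing is confirmation in 8.9.1.
- **That section 8.8 discards those scores.** It drops missing ratings, and a collected Day 2 score is not missing.
- **That healing of one area cuts short the follow-up of the other.** Section 6.3 is ambiguous, and it can be read as requiring all of a participant's areas to have healed.

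**Conclusion.** The point holds as a should-fix. As written, Day 3 data are missing because of healing, and the plan does not state how an early last-day score enters the primary model. With that score in the Day 5 slot, Day 0 vs 3 and Day 1 vs 3 tend to be understated and Day 3 vs 5 overstated, while Day 0 vs 5 holds. Day 0 vs 5 is understated if off-schedule scores or early healers are left out.

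With the last-day score in the Day 5 slot and other scores kept on their own days, the simulated Day 3 vs 5 error runs from about 0.5 mm or less (few early healers, or gradual healing) to about 5 mm (20% healed abruptly by Day 2). The upper end is half the plan's 10 mm minimal difference. A flat statement that the contrasts are biased by a given amount is not supported: the documents give neither the rate nor the pattern of early healing. The simulations use assumed VAS data, and the ordinal models for the Likert outcomes were not simulated. In section 4 of the working, carrying forward matches the truth by construction, because healed areas were assumed to stay healed.

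The conflict between sections 8.3 and 5.4 comes first. It decides whether early healers are analysed at all, and in the gradual-healing runs excluding them moved the results more than the Day 5 coding did.

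**What to change.** 1. In 8.8 and 8.9.1, state per target area that once an area is recorded as fully healed, its last-day scores are used for every remaining scheduled model day. Healing on Day 1 or 2 fills Days 3 and 5; healing on Day 3 or 4 fills Day 5. A score taken on Day 1 or 3 also stays on its own day.
2. Add a sensitivity analysis on observed days only.
3. Reconcile 8.3 with 5.4 so that early healers stay in the analysis.
4. Clarify in 6.3 whether the last day is set by one target area or by all of a participant's areas.

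The cost is a few sentences and a few lines of code, with no new data. The rule should be fixed before data are seen. The one downside is the assumption that a healed area stays healed through Day 5, at most four days; the observed-days analysis shows how far the results depend on it.
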